**Table 3: Definitions for Treatment Start and End Dates by Treatment Period (Continued)**

| Treatment Period | Treatment Start Date   | Treatment End Date   |
|------------------|--|--|
| Entire Study     | The date at which a randomized subject takes the first dose of the DM study drug | The date at which a randomized subject takes the last dose of the study drug.
Missing last dose date will be handled the same way as mentioned above. |

Notes:

1. Pediatric subjects only participate in the double-masked period.
2. For each treatment period, the treatment end date will be set to missing if the treatment start date is missing.

#### 4.1.3. Study Day

The *study day* describes the relative day of an observation starting with the reference date designated as Study Day 1. In this study, the treatment start date is the reference date. Thus, the study day will be calculated as:

- For days prior to the treatment start date, Study Day = Date – Treatment Start Date
- For days on/after the treatment start date, Study Day = Date – Treatment Start Date + 1

#### 4.1.4. Out-of-Window Measurements, Analysis Visit, and Analysis Window

*Analysis visit* is a timing variable to be used for analyses involving visits. For each analysis visit, an *analysis window* is set up to determine the analysis visit to which a measurement should be mapped (Table 4).

The analysis visit of a measurement will be determined based on the study day of the measurement and specified analysis windows and is not necessarily the same as the study visit at which the measurement was collected. For example, an out-of-window measurement collected at the Week 1 study visit will be mapped to the Week 6 analysis visit, if the study day of the measurement falls into the analysis window of Week 6.

**Table 4: Analysis Visit and Analysis Window**

| Analysis Visit Name
(Target Day) | Protocol Visit Window | Analysis Window                       |                                   |                  |
|-------------------------------------|-----------------------|---------------------------------------|-----------------------------------|------------------|
|                                     |                       | Iris Color,
Eyelash, and
Eyelid | Ophthalmoscopy
and Vital Signs | Other Parameters |
| Baseline (Day 1)                    | [1, 1]                | - 1]                                  | - 1]                              | - 1]             |
| Week 1 (Day 8)                      | [6, 10]               | NA*                                   | NA*                               | [2, 22]          |
| Week 6 (Day 43)                     | [40, 46]              | NA*                                   | NA*                               | [23, 61]         |

**Table 4: Analysis Visit and Analysis Window (Continued)**

| Analysis Visit Name
(Target Day) | Protocol
Visit
Window | Analysis Window                       |                                   |                                   |
|-------------------------------------|-----------------------------|---------------------------------------|-----------------------------------|-----------------------------------|
|                                     |                             | Iris Color,
Eyelash, and
Eyelid | Ophthalmoscopy
and Vital Signs | Other
Parameters               |
| Month 3 (Day 91)                    | [84, 98]                    | [2, day of Month 3 Visit]             | [2 -, day of Month 3 Visit]       | [62, day of Month 3 Visit]        |
| Month 6 (Day 181)                   | [171, 191]                  | [First Day of OL period + 1, 225]     | NA*                               | [First Day of OL period + 1, 225] |
| Month 9 (Day 271)                   | [261, 281]                  | [226, 315]                            | NA*                               | [226, 315]                        |
| Month 12 (Day 361)                  | [351, 371]                  | [316 -                                | [Day of Month 3 Visit + 1, -]     | [316 -                            |

\*Not collected at this visit.

If there are two or more visits that fall into the same analysis window, then the visit closest to the target assessment day will be selected for that visit window. In the case that two visits are equidistant to the target assessment day, i.e., one is before and one is after the target assessment day, the later one will be selected for that visit.

For analyses of IOP involving post-baseline visits, if there are two or more visits that fall into the same analysis window of a post-baseline visit, then the visit in which IOP are measured at all the scheduled timepoints (8:00, 10:00, and 16:00) will be selected for that analysis visit first, before applying the above rule.

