8.5. Subject Withdrawal Criteria

An early termination occurs when a subject who provides written informed consent ceases participation in the study, regardless of circumstances, before the completion of the study. Subjects may be voluntarily discontinued from study medication or withdrawn from the study at any time for any reason. In addition, the Principal Investigator or Medical Monitor may discontinue the study drug administration or terminate a subject's study participation due to any of the following reasons:

- AE (e.g., not compatible with study continuation)
- Non-compliance with study drug
- Lack of efficacy (e.g., IOP exceeds 34 mmHg in either eye after randomization)
- Progressive disease

- Protocol deviation (e.g., not fulfilling eligibility criteria)
- Pregnancy
- Voluntary withdrawal by subject at any time for any reason
- Lost to follow-up (e.g., no contact is possible)
- Death
- Other

If the study drug administration is discontinued prior to Visit 5, they should be encouraged to still participate in follow-up study visits until Visit 5 on an observational basis.

[figure not shown]
If the study drug administration is discontinued prior to Visit 5, then to the extent possible, all procedures for Early Termination will be performed on the day of early drug discontinuation as per [Table 3](#) (for adult subjects) or [Table 4](#) (for pediatric subjects). Subjects who are discontinued from the study early will not be replaced.

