### 6.2.2. Safety Measures

Descriptive summaries of safety measures will be based on observed data only. No imputation of missing scores will be implemented.

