## **9.6. Vital Signs**

Resting blood pressure (systolic and diastolic) and pulse rate and their change from baseline will be summarized by treatment, analysis visit, and study period (double masked and open-label).

A listing for vital signs will be provided.

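### After an early drug stop, the Month 3 by-visit tables for vital signs, fundus and iris/eyelash/eyelid can drop the exam made at the stop and report an off-drug Visit 5 exam under the drug received

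*SAP*

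**What the plan says.** **Protocol 8.5 (and the note in 7.4.6).** When drug is stopped before Visit 5, to the extent possible "all procedures for Early Termination will be performed on the day of early drug discontinuation". Of the same subjects the protocol says "they should be encouraged to still participate in follow-up study visits until Visit 5 on an observational basis". A subject can thus have two sets of safety exams in the masked period, one at drug stop and one later, off drug.

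**SAP 4.1.4, Table 4.** For iris color, eyelash and eyelid the Month 3 window is "2, day of Month 3 Visit". The ophthalmoscopy and vital-signs cell has the same limits. Neither column has a Week 1 or Week 6 window. BCVA and slit lamp, under other parameters, have three windows: Days 2–22, Days 23–61, and Day 62 to the Month 3 visit. When a window holds more than one visit, "then the visit closest to the target assessment day will be selected for that visit window". If two are equally distant, "the later one will be selected for that visit". The extra rule that favours complete visits applies to IOP only.

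**SAP 6.2.2 and Section 9.** "Descriptive summaries of safety measures will be based on observed data only", grouped by actual treatment received. For vital signs, blood pressure and "pulse rate and their change from baseline will be summarized by treatment, analysis visit". The retina/macula/choroid and vitreous shift table is planned for Month 3 only (SAP 9.4). No on-treatment limit is given for exam findings. Adverse events do have one: SAP 4.4.1 ends treatment emergence 2 days after the treatment end date.

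**Month 12.** For ophthalmoscopy and vital signs the Month 12 window opens at "Day of Month 3 Visit + 1" and has no stated upper limit.

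**The concern.** The safety objective is a comparison of DE-117 with Timolol. For a subject who stopped drug weeks before Visit 5, the Month 3 row would show a reading taken after the drug effect may have worn off, attributed to the drug and not flagged. If more subjects stop early in one arm and then return, that arm's by-visit tables move toward no effect.

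Two measures are most exposed.

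- **Vital signs** are scheduled only at Visits 1, 2, 5 and 8/early termination. For an early stopper, the reading at drug stop is the only protocol-scheduled post-baseline value close to dosing. SAP 9.6 plans by-visit summaries and a listing, with no threshold or worst-value table.
- **Adult ophthalmoscopy** is dilated at early termination but not scheduled as dilated at Visit 5. The rule can therefore replace a dilated exam at drug stop with an undilated off-drug exam, although macular edema is an event of special interest.

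The Month 12 window raises a separate labelling problem, because exit exams after very short open-label exposure share a row with full-exposure exams.

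**Working it through.** The plan states no figure for this, so the check applies the selection rule day by day.

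**Inputs.** Targets are Days 8, 43 and 91. The protocol windows 8±2, 43±3 and 91±7 give Days 6–10, 40–46 and 84–98, as in Table 4. Let *e* be the day of the exam at drug stop and *v* the day of Visit 5, with *e* < *v*.

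**Vital signs, ophthalmoscopy, iris/eyelash/eyelid.** The exam at drug stop is kept only if |*e* − 91| < |*v* − 91|, since a tie goes to the later visit.

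- *v* ≤ 91: any earlier *e* is further from Day 91, so it is never kept. With *v* = 91 that is 0 of 89 possible days (2–90).
- *v* = 95: kept for *e* = 88–94, 7 days.
- *v* = 98: kept for *e* = 85–97, 13 days.
- For *v* = 92 to 98 the kept days number 1 + 3 + 5 + 7 + 9 + 11 + 13 = 49.
- All combinations for *v* = 84 to 98: the sum of (*v* − 2) is 15 × 91 − 30 = 1,335. Share kept: 49 / 1,335 = 3.7%.
- The earliest *e* ever kept is Day 85.

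These are shares of calendar-day combinations, not of subjects. A Visit 5 later than Day 98 would move the Day 85 limit earlier.

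**BCVA and slit lamp**, with visits on Days 8, 43 and 91 and the stop on any other day from 2 to 90 (87 days):

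| Window | Loses to a later, off-drug visit | Loses to an earlier, on-drug visit |
|---|---|---|
| Week 1 (Days 2–22) | 6 (Days 2–7) | 14 (Days 9–22) |
| Week 6 (Days 23–61) | 20 (Days 23–42) | 18 (Days 44–61) |
| Month 3 (Days 62–90) | 29 | 0 |
| Total | 55 | 32 |

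Visit 5 itself displaces the exam only for stops on Days 62–90. In 32 of 87 cases the record kept is an earlier on-drug visit. Over all in-window visit days, the exam at drug stop is kept in about 9.5% of combinations.

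**Size.** The shift in an arm's Month 3 mean is *p* × *d*. Here *p* is the share of subjects in the row whose exam was displaced by an off-drug one, and *d* is the mean difference between their two readings. The documents give neither. If *p* is assumed to be 2% to 10%, each 1 beat/min of *d* moves the arm mean by 0.02 to 0.10 beats/min.

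**Month 12.** An open-label exit on Day 110 falls in the Month 12 window for fundus and vital signs, although the target is Day 361 (361 − 110 = 251 days later). For other parameters, Month 12 opens only at Day 316.

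**The case against.** The strongest reply is that the affected tables are a small part of the safety reporting. SAP Section 9 tabulates and lists adverse events leading to drug discontinuation. It gives ocular inflammation, macular edema and cosmetic changes their own summaries; the macular edema summary includes BCVA change at onset. It summarizes and lists BCVA changes of 0.2 logMAR or more and clinically significant slit-lamp worsening. It lists cup/disc increases, optic nerve worsening, normal-to-abnormal fundus changes, eyelid sulcus changes and vital signs. None of these is stated to be limited to the selected record, and no safety testing is planned. This stands. A reader might infer that the rule hides the changes that made subjects stop. The documents do not support that reading. It is, however, also not stated that these outputs use all records.

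A reader might also infer that the exam at drug stop is always lost. It is not. Attendance at Visit 5 after stopping is only encouraged, and a subject who does not return keeps the early exam (though the window's upper limit, the day of the Month 3 visit, is then undefined). Some stops from Day 85 onward also keep it.

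'On-drug' is itself approximate: the exam is done to the extent possible on the day of stopping, and SAP 3.4 ties exit assessments to ending study participation.

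Retaining observed off-drug data is consistent with the SAP's IOP rule, which censors after non-study IOP-lowering therapy and not after stopping drug. That is fair, but the problem here is selection and labelling, not retention.

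For Month 12, the schedules already head that column as exit or early termination, and the open-label period has one arm, so the between-arm argument does not apply. The point there is labelling only.

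**Conclusion.** The concern holds in limited form. For subjects who stop before about Day 85 and attend Visit 5 in its window, Table 4 followed exactly drops the exam at drug stop from the Month 3 summaries of vital signs, ophthalmoscopy (including the Month 3-only shift table) and iris/eyelash/eyelid. It reports the off-drug exam under the drug received. For BCVA and slit lamp the effect is weaker: Visit 5 competes only from Day 62, and earlier exams lose to Week 1 or Week 6 visits, some of them on drug.

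The distortion is confined to by-visit descriptive tables. Its direction, toward no effect in the arm with more early stoppers who return, assumes that drug effects fade after stopping. No amount can be given. A reader might want to quote a bias in mean pulse, but that requires a discontinuation rate, a return rate and a pulse change in early stoppers, and the documents supply none of them.

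The Month 12 mislabelling of early open-label fundus and vital-sign exits is a separate and smaller point. The change is still worth making before unmasking, because the Timolol comparison is a stated safety objective and the data needed are already collected.

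**What to change.** In SAP 4.1.4 and Section 9:

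1. Define an on-treatment safety exam as one on or before the treatment end date + 2 days, the limit the SAP already uses for treatment-emergent adverse events.
2. Exclude off-treatment exams from the by-visit on-treatment rows and show them in a separate post-treatment row.
3. Add *last on-treatment* and *worst on-treatment* rows that use all scheduled, unscheduled and early-termination records. Do not move early exams into the Month 3 row instead: its window opens on Day 2, so that would mix short and full exposures.
4. State that the threshold summaries and listings use all records, not only the record selected for an analysis visit.
5. Label fundus and vital-sign exit exams before Day 316 as *Early termination*, not Month 12.

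The cost is SAP wording, a few extra table rows, and slightly fewer subjects in the Month 3 and Month 12 rows. No new data are needed.

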#### 4.1.5. Extent of Exposure

The *extent of exposure* to study medication will be assessed by duration of treatment exposure, derived as:

$$\text{Duration of treatment exposure} = \text{Treatment end date} - \text{Treatment start date} + 1$$

### 4.2. Endpoint-Related Definitions

#### 4.2.1. Study Eye and Fellow Eye

The study eye will be the eye that qualifies per eligibility criteria at Visit 2. If both eyes meet the eligibility criteria, the eye with the higher mean diurnal IOP at Visit 2 will be designated as the study eye. If both eyes meet the eligibility criteria and have the same mean diurnal IOP, the right eye will be designated as the study eye. The other eye will be the non-study eye, or fellow eye.

#### 4.2.2. Baseline Score

The *baseline score* is the observed measurement at Visit 2 (Baseline). If a baseline score is missing, the last observed measurement or derived score prior to the first dose of study medication will be used to impute the baseline score.

### 4.2.3. Change and Percent Change from Baseline

The change and the percent change from baseline in a measure at a post-baseline visit will be derived as:

- Change = (Score at the Post-Baseline Visit) – (Baseline Score)
- Percent Change from Baseline =  $100 \times \text{Change} / (\text{Baseline Score})$

## 4.3. Efficacy-Related Definitions

### 4.3.1. Response Endpoint and Response Rate

Four IOP response endpoints ([Table 5](#)) will be evaluated at each post-Baseline visit during the double masked-period (Week 1, Week 6, or Month 3) and open-label period (Month 6, Month 9, and Month 12) in this study:

**Table 5: Response Endpoints**

| Response Endpoint           | Response criteria in mean diurnal IOP       |
|-----------------------------|---|
| IOP 20% response            | Percent reduction from Baseline $\geq 20\%$ |
| IOP 25% response            | Percent reduction from Baseline $\geq 25\%$ |
| IOP 30% response            | Percent reduction from Baseline $\geq 30\%$ |
| IOP $\leq 18$ mmHg response | Mean diurnal IOP $\leq 18$ mmHg             |

For a response endpoint, the response rate at a post-Baseline visit is calculated as the proportion of subjects who met the response criterion at the post-baseline visit.

The open-label analysis of these endpoints will be performed only at the end of this study when all adult subjects complete their Month 12 Visit.

## 4.4. Safety-Related Definitions

### 4.4.1. Adverse Event

Under Protocol 011709IN, an AE is defined as any untoward medical occurrence that occurs in a study subject, regardless of the causal relationship with the study treatment. An *on-study* AE can occur any time after the date of informed consent through the last study visit. An AE will be considered as *treatment-emergent* if the onset date of the AE occurred on or after the treatment start date till up to 2 days (twice the scheduled dosing interval) after treatment end date.

Treatment-emergent AEs (TEAEs) are a subset of on-study AEs. Both on-study and TEAEs will be collected, but only TEAEs will be tabulated.

The severity of each AE will be graded by the Clinical Investigator as Mild, Moderate, or Severe. AEs will also be rated by the Investigator as to their causality/relationship to the study drug.

Each AE will be classified into a system organ class (SOC) and coded to a preferred term (PT) using Medical Dictionary for Regulatory Activities (MedDRA), Version 21.1 published in 2018.

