21. Presence or history of any disease or condition that, in the opinion of the study Investigator, may put the subject at significant risk (such as contraindication to the use of Timolol Maleate Ophthalmic Solution 0.5%), may confound study results, or may interfere significantly with the subject's participation in the study (e.g., recurrent corneal erosion syndrome, uncontrolled cardiovascular disease etc.).
22. Any decision by the Investigator or Medical Monitor to terminate a subject in screening or declare any subject ineligible for any sound medical reason.

Investigational product, dosage and mode of administration:

Subjects will be assigned in a 1:1 ratio to the DE-117/Vehicle arm and Timolol Maleate arms as follows:

Investigational Product:

DE-117 Ophthalmic Solution contains 0.002% DE-117. Each 2.5 mL bottle of DE-117 Ophthalmic Solution 0.002% contains 50 µg of DE-117. In addition,

Vehicle:

The vehicle is the same as the vehicle used in DE-117. [REDACTED]

Comparator:

Timolol Maleate Ophthalmic Solution 0.5% contains the active ingredient, timolol 5 mg/mL and the preservative BAK 0.01%. Other ingredients include monobasic and dibasic sodium phosphate and purified water. The pH is adjusted to 6.5 to 7.5 with sodium hydroxide.

During the Double-Masked Treatment Period subjects will be instructed to instill one drop of study medication from bottle labeled “evening” in each eye at 20:00 and one drop of study medication from bottle labeled “morning” in each eye at 08:00 starting in the evening of Visit 2 (Baseline, Day 1) through the morning before Visit 5 (Month 3). After the Visit 5 (Month 3), adult subjects will be instructed to instill one drop of study medication from bottle labeled “evening” in each eye at 20:00 through the morning before Visit 8 (Month 12). Note: Open-label DE-117 Ophthalmic Solution 0.002% will be dispensed at Visits 6 and 7.

Route of Administration of Investigational Product: Topical ocular**Duration of the Study:**

Adult subjects: The study duration includes up to 5 weeks Screening Period, a 3-month Double-Masked Treatment Period, and a 9-month Open-Label Treatment Period.

Pediatric subjects: The study duration includes up to 5 weeks Screening Period and a 3-month Double-Masked Treatment Period.

Criteria for Evaluation:**Efficacy:**

Efficacy will be assessed by evaluating IOP at scheduled time points (08:00, 10:00 and 16:00) at all scheduled visits with the exception of the Screening visit.

Safety:

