Following completion of the Double-Masked Treatment Period, adult subjects will convert to a single DE-117 0.002% QD arm at Visit 5 (Month 3). This Open-Label Treatment Period will last 9 months, starting at the end of the Visit 5 (Month 3) and ending at Visit 8 (Month 12). All subjects will dose with DE-117 0.002% QD at 20:00 (\pm 60 min) starting in the evening of Visit 5 (Month 3) and ending the evening before Visit 8 (Month 12). No vehicle will be dosed during the Open-Label Treatment Period.

The study will evaluate the efficacy and safety of DE-117 Ophthalmic Solution 0.002% compared with Timolol Maleate Ophthalmic Solution 0.5% in subjects with glaucoma or OHT through Month 3 and will provide additional safety data through Month 12.

IOP will be measured at 08:00, 10:00 and 16:00 (\pm 60 min). At these scheduled visits, BCVA and slit-lamp biomicroscopy will be performed just prior to the 08:00 IOP measurement.

Ophthalmoscopy (fundus examination) will be performed after the 16:00 IOP measurement.

Vital signs (resting blood pressure and pulse rate) will be collected in sitting position anytime at Visit 1, and approximately 08:00 for Visits 2, and 5 before the morning dose. Vital signs will also be collected at Visit 8 at approximately 08:00.

Pharmacogenomics/genomics:

Subjects who consent to the optional pharmacogenomics/genomics laboratory study will provide a blood sample for future testing. The purpose of this exploratory research is to identify possible genetic markers associated with the study medication(s) and/or ocular conditions.

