- An authorized unmasked study staff member, other than the Investigator or Examiner should query the subject regarding dosing compliance.
- Query the subject regarding AEs.
- Perform vital signs (blood pressure/pulse rate) measurements at approximately 08:00.
- As per Schedule of Events and Procedures [Table 3](#) (for adult subjects) **or** [Table 4](#) (**for pediatric subjects**), perform the following procedures or assessments immediately before the 08:00 IOP measurement (all ophthalmic procedures to be performed in both eyes):
 - BCVA (before the 08:00 IOP measurement)
 - If more than 10 letters in BCVA were lost compared to the screening visit, then refraction should be performed again.
 - Biomicroscopy (before the 08:00 IOP measurement)
- Perform IOP measurement at 08:00 (±60 min).

- Instill study medication/eye drop after the 08:00 IOP measurement in both eyes (**for pediatric subjects, the investigator may elect to dose only one eye, the study eye**). An authorized unmasked study staff should make sure the instillation is performed.
- Perform IOP measurement at 10:00 and 16:00 (± 60 min).
- Perform ophthalmoscopy in both eyes immediately after the 16:00 IOP measurement.
- As per Schedule of Events and Procedures [Table 3](#) (for adult subjects) **or** [Table 4](#) (**for pediatric subjects**), perform the following procedures or assessments at any time during this visit.
 - Assess any changes from baseline in Iris color, Eyelash, Eyelid and take front view and side view photographs of each eye. The following six (6) photos are required at this visit as follows:

- Obtain urine and perform urine pregnancy test, if the subject is a female of child-bearing potential.
- An authorized unmasked study staff member, other than the Investigator or Examiner, must:
 - Collect all used and unused bottles of study medication.

Note:

- **If the study drug administration is discontinued prior to Visit 5, the subject should be encouraged to still participate in follow-up study visits until Visit 5 on an observational basis.**
- **If the study drug administration is discontinued prior to Visit 5, then to the extent possible, all procedures for Study Exit/Early Termination as per [Table 3](#) (for adult subjects) **or** [Table 4](#) (**for pediatric subjects**) will be performed on the day of early termination. Subjects who are discontinued from the study early will not be replaced.**

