**Table 3: Definitions for Treatment Start and End Dates by Treatment Period**

| Treatment Period                    | Treatment Start Date   | Treatment End Date   |
|-------------------------------------|--|--|
| Double-Masked (DM) Treatment Period | The date at which a randomized subject takes the first dose of the DM study drug       | 
The date at which a randomized subject takes the last dose of the DM study drug. If the date of the last dose is missing and the subject does not receive any OL study drug:
 
 
• The day before the Visit 5 (Month 3) date will be considered the treatment end date for subjects who completed the Month 3 Visit
 
• The day before the Exit Visit date will be used for subjects who prematurely discontinued from the study before Visit 5 (Month 3). If the Exit Visit date of a non-completer is not available, then the day before the last available visit date will be considered the treatment end date
 
 |
| Open-Label (OL) Treatment Period    | The date at which a randomized adult subject takes the first dose of the OL study drug | 
The date at which a randomized adult subject takes the last dose of the OL study drug. If the date of the last dose is missing:
 
 
• The day before the Visit 8 (Month 12) date will be considered the treatment end date for subjects who completed the Month 12 Visit
 
• The day before the Exit Visit date will be used for subjects who prematurely discontinued from the study during OL period. If the Exit Visit date of a non-completer is not available, then the day before the last available visit date will be considered the treatment end date
 
  |

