### 9.1. Adverse Events

AEs, SAEs, SARs, serious SARs, and significant AEs (AEs leading to study drug discontinuation and AEs leading to death) will be tabulated by type of AEs by treatment arm using actual treatment received for all AEs, ocular AEs, and non-ocular AEs separately.

Besides the overall AE summary, AEs, SAEs, SARs, serious SARs will be tabulated by SOC and preferred term for all AEs, ocular AEs, and non-ocular AEs separately. A subject who experienced multiple AEs within a SOC or preferred term will be counted only once for that SOC or preferred term. Non-serious AEs (including number of events) and ESIs will also be summarized by SOC and preferred term.

All the AE summaries will be performed for double-masked, open-label, and entire study periods separately. For double-masked period summaries, overall AE summary, summary of AE by SOC and PT, SAEs, SARs, and serious SARs will also be tabulated on pediatric subjects separately. For open-label and entire study period summaries, tabulations by treatment received during double-masked period will be provided as well as overall summary for subjects exposed to DE-117. So, for subjects who exposed to the Timolol arm during the double-masked period, their AE summaries under the Overall DE-117 column will be those AEs that started during the open-label treatment period.

AEs, SAEs, SARs, serious SARs, ocular AEs, AEs leading to death, AEs leading to study drug discontinuation, non-TEAEs, and ESIs, if any, will be listed separately.

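### The treatment-emergent AE window does not stop at the switch to open-label DE-117, so in Timolol adults events dated to Visit 5 or the two days after it can be tabulated under the wrong drug

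*SAP*

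**What the plan says.** SAP 4.4.1 defines an AE as treatment-emergent when its onset "occurred on or after the treatment start date till up to 2 days (twice the scheduled dosing interval) after treatment end date". Only treatment-emergent events are tabulated.

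SAP Table 3 defines treatment dates three times: for the double-masked period, the open-label period and the entire study. The double-masked end date is "The date at which a randomized subject takes the last dose of the DM study drug". The open-label start date is "The date at which a randomized adult subject takes the first dose of the OL study drug". Section 4.4.1 does not say which set it uses.

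SAP 9.1 produces AE summaries separately for the three periods. For subjects who had Timolol in the masked period, "their AE summaries under the Overall DE-117 column will be those AEs that started during the open-label treatment period".

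The Protocol sets the doses around the switch. Section 7.1 has open-label DE-117 taken at 20:00, "starting in the evening of Visit 5 (Month 3) and ending the evening before Visit 8 (Month 12". For the masked drug, the instruction "Instill study medication/eye drop after the 08:00 IOP measurement in both eyes" stands in Protocol 7.4.5 (Visit 4) and is repeated in 7.4.6 for Visit 5. The Protocol synopsis instead has masked dosing run "through the morning before Visit 5 (Month 3". Protocol 12.1.1.2 has the duration of each AE recorded in dates.

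SAP Table 4 does make a clean cut for visit-based data. Month 3 closes on the day of the Month 3 visit, and the Month 6 window for most parameters is "First Day of OL period + 1, 225".

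**The concern.** Timolol adults who enter the open-label period change drug on the evening of Visit 5. An AE window that runs two days past the last masked dose crosses that change, and nothing in SAP 4.4.1 stops it. Two kinds of misattribution can follow.

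- **In the randomized table.** An event that starts after the first DE-117 dose can be counted under double-masked Timolol. DE-117 subjects do not change drug, so this error has one direction: it can only add post-DE-117 events to the comparator and narrow any DE-117 excess.
- **In the Overall DE-117 column.** An event dated to Visit 5 can be counted as DE-117 in a subject who had taken only Timolol. Visit 5 has an AE query, vital signs, biomicroscopy before the 08:00 IOP and ophthalmoscopy after the 16:00 IOP. All are scheduled before the evening dose, so findings may well carry that date.

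The safety objective is the comparison of DE-117 with Timolol, and macular edema is an event of special interest, so a single misplaced case could be noticed.

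**Working it through.** **The 2-day figure.** SAP 4.4.1 explains it as twice the dosing interval.
- Once daily: 2 × 24 h = 48 h = 2 days. This reproduces the figure.
- Twice daily (Timolol): 2 × 12 h = 24 h = 1 day. This does not. A 1-day tail would still cross the switch, so shortening it is no cure.

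**Windows under period-specific dates.** Inputs: Visit 5 on Day 91; last masked dose that morning (Protocol 7.4.6); first open-label dose that evening (7.1); Visit 8 on Day 361, so last open-label dose on Day 360.
- Double-masked: Day 1 to Day 91 + 2 = Days 1–93.
- Open-label: Day 91 to Day 360 + 2 = Days 91–362.
- Dates in both: Days 91, 92 and 93.

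**Which of these are wrong in the Timolol column.** Day 91 belongs to the masked period until 20:00. Days 92 and 93 follow the first DE-117 dose.
- Share: 2/93 = 2.2%. Over the Visit 5 window (Day 84 to Day 98) it runs from 2/86 = 2.3% to 2/100 = 2.0%.
- In clock time, the Timolol window holds 4 + 48 = 52 h after the first DE-117 dose.

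**If the last masked dose was the day before Visit 5** (one reading of the synopsis): the window is Days 1–92, only Day 92 follows the switch, and the share is 1/92 = 1.1%.

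**Windows under entire-study dates.** The tail follows only the final dose, so the problem on Days 92–93 goes. Period is then left to the SAP 9.1 wording about events starting in the open-label period.

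**The Visit 5 date, either reading.** The open-label start is a calendar date, and AEs are recorded in dates. An event dated to Visit 5 therefore falls on or after that start, although 20 h of the day precede the 20:00 dose.

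**Other rules that might help.**
- SAP 9 puts subjects who took both drugs with DE-117, but only for the masked period.
- SAP 7.7 takes a Timolol subject's DE-117 exposure as total days minus Timolol days, without overlap. AE counts and exposure days then do not match at the switch.
- SAP 9.1 adds open-label events to Overall DE-117 but removes none from the masked Timolol column.

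**After the change proposed below:** double-masked Days 1–91, open-label Days 92–362, overlap zero.

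**The case against.** The strongest reply is that SAP 4.4.1 can be read with the entire-study dates. The 2-day explanation fits that reading for adults, who are on once-daily DE-117 at their final dose, and the double count then disappears. This stands as far as it goes: the double count depends on the period-specific reading. That reading fits the separate tables in SAP 9.1 better, but the SAP does not state it. The entire-study reading leaves the Visit 5 date unresolved.

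A short tail is also a defensible allowance for carry-over. The Timolol package insert in Protocol Appendix E says that IOP lowering can last up to 24 hours after one dose, so an event soon after the switch is not necessarily due to DE-117. This stands too, and it is a real cost of removing the tail.

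Further, SAP 6 plans no statistical tests on safety measures, AEs are also listed, and investigators rate relatedness. A subject with several events in one preferred term counts once, so some misplaced events would change nothing. No visit is scheduled in the two days after Visit 5, so those dates would hold mainly events that subjects report. All of this limits the consequence.

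A reader might infer that three of 93 days (3.2%) are wrong in the randomized table. They are not: Visit 5 itself belongs there. A reader might also object that events found at Visit 2 before the first dose become treatment-emergent by date. That affects both arms alike and gives no reason to change the rule.

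**Conclusion.** The point holds in limited form. SAP 4.4.1 does not name the dates it uses. Under period-specific dates, the rule places events from two dates after the switch (one, if masked dosing ended the day before Visit 5) under double-masked Timolol and again under open-label DE-117. This is about 2% of the double-masked days at risk, and it concerns only Timolol adults who switch. For DE-117 subjects the overlap repeats an event under the same drug, and pediatric subjects do not switch. Under either reading, an event dated to Visit 5 can enter the Overall DE-117 column before any DE-117 was taken. That column is pooled and uncontrolled, so this part does not touch the randomized comparison.

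It is tempting to put a number of misplaced subjects on this. The documents give no AE rates, so none can be computed. Each subject misplaced would move an arm of 200 by 1/200 = 0.5 percentage points. With safety descriptive, the effect is probably small, but the rule can be corrected at almost no cost.

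**What to change.** In SAP 4.4.1, state which Table 3 dates apply, and then:

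- For subjects who take open-label drug, end the double-masked window on the Visit 5 date, with no 2-day tail, and start the open-label window the next day. This matches Table 4.
- Use the same cut for the Overall DE-117 column in SAP 9.1.
- Keep the 2-day tail for subjects who take no open-label drug and after the final open-label dose.

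The Protocol synopsis and Protocol 7.4.6 should also be reconciled on when masked dosing ends, since this sets the double-masked end date.

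The cost is SAP wording and derivation code, with no new data. There is a trade-off. An event that starts on the Visit 5 evening after the first DE-117 dose is assigned to the masked period, and a Timolol carry-over event on the next two days is assigned to the open-label period. An exception based on onset time is not advised, because AEs are recorded in dates and it could seldom be applied.
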